10.5. Efficacy Analysis

PK is a surrogate for efficacy, since a titer of ≥ 0.5 IU/mL is well-established as protective against the rabies virus. RVNA titers will be listed for each subject, and summary statistics for each timepoint presented by treatment group.

10.5.1. Primary PK Analysis

The primary efficacy analysis will be based on the primary PK population.

The primary hypothesis is that the proportion of subjects receiving BPL HRIG + active vaccine with an anti-rabies titer of ≥ 0.5 IU/mL will not be less than the corresponding proportion for subjects receiving comparator HRIG + active vaccine, by more than 0.1 at Visit 6. The Farrington and Manning test statistic will be used to assess the statistical comparison at a one-sided significance level of 0.025. It will be concluded that the BPL HRIG is non-inferior to the comparator HRIG if the lower limit of an exact binomial 95% confidence interval calculated from the Farrington-Manning score test is greater than the *a priori* set -10% non-inferiority margin.

An additional analysis will be performed to assess the impact of dosing/PK sampling not being performed on the designated day. See Section 10.7.2.

10.5.2. Hypothesis for the Primary PK Analysis

The null hypothesis is $p-p_0 \leq -0.1$;

The alternative hypothesis is $p-p_0 > -0.1$,

where p is the proportion of subjects with anti-rabies titer of ≥ 0.5 IU/mL at Visit 6 in subjects receiving BPL HRIG + vaccine and p_0 is the proportion receiving comparator HRIG + vaccine.

We reject the null hypothesis at the one-sided 0.025 significance level, and conclude that $p-p_0 > -0.1$, if the lower bound of an exact 95% binomial confidence interval exceeds -0.1.

10.5.3. Secondary PK Analysis

Secondary efficacy analyses 2 and 5 will be based on the secondary PK population.

Secondary efficacy analyses 1, 3, and 4 will be based on the primary PK population, since timepoints post-Visit 6 are not included in these analyses.

The secondary PK endpoints will be analyzed as follow:

- 1) the assessment AUC_{0-7d} for BPL HRIG and vaccine versus comparator HRIG and vaccine using a non-inferiority margin of 20%.
- 2) the geometric mean titers (GMTs) for RVNA titer up to peak serum level after administration of BPL HRIG and vaccine or comparator HRIG and vaccine will be assessed using a mixed model repeated measure [MMRM] analysis.
- 3) the proportion of subjects reaching anti-rabies antibody titer of ≥ 0.5 IU/mL at Visits 3-6 after administration of BPL HRIG and vaccine versus comparator HRIG and vaccine will be assessed using a generalized estimated equation [GEE] for a repeated measure analysis.
- 4) the proportion of subjects reaching anti-rabies antibody titer of \geq the lower limit of quantification (LLOQ) of the assay at Visit 3-6 after administration of BPL HRIG and

vaccine versus comparator HRIG and vaccine will be assessed using a generalized estimating equation [GEE] for a repeated measure analysis.

- 5) the GMTs for anti-rabies antibody titer at Visits 6-9 will be compared between treatment groups. Descriptive statistics and visual inspections will be reported as appropriate. No formal hypothesis testing will be performed.

10.5.4. Exploratory PK Analysis

The PK parameters for anti-rabies antibody concentrations as described in [Section 8.1.3](#) will be statistically compared as appropriate between treatment groups.

Non-compartmental PK methods will be utilized to calculate the subject level PK parameters. C_{max} , AUC_{0-t} , AUC_{0-7d} , $AUC_{0-\infty}$, apparent terminal rate constant (λ_z), and $t_{1/2}$ will be dose normalized by dividing the raw PK parameters by the actual dose the subject received. A t-test will compare the PK and dose-normalized PK parameters between treatment groups. Log-transformations will be performed as necessary during statistical analysis when appropriate.

10.6. Safety Analysis

The safety analysis will be based on the safety population. The general strategy of the safety evaluation will be to examine the summaries for any clinically relevant imbalance of safety events between the treatment groups. Safety parameters for the two treatment groups will be compared descriptively. Summary data will be presented by Treatment Group. No formal hypothesis testing will be carried out.

10.6.1. Adverse Events

Adverse events (AEs) will be reported by the MedDRA system organ class and preferred term. Only treatment-emergent AEs, defined as those events with onset date from dosing with BPL HRIG / vaccine or comparator HRIG / vaccine will be included in the summary tables. All AEs will be included in the data listings.

Treatment-related AEs will be defined as events recorded as having a possible, probable or very likely/certain causality to treatment. AEs leading to withdrawal will be defined as events where the subject's participation in the study was discontinued as a result of the AE.

AEs will be summarized descriptively for all subjects and by treatment group. The denominator used for the calculation of percentages will be the number of subjects in the safety population per treatment group. For all AE summaries described below, counting will be performed by subject and event. For counts by subject, subjects experiencing the same event more than once

will have that event counted only once within each system organ class and once within each preferred term.

The following summaries of treatment-emergent AEs will be provided:

Summary of AEs

- 1) The number and percentage of subjects reporting AEs, serious AEs, study medication related AEs, AEs leading to withdrawal and AEs leading to death.
- 2) The number of AEs, serious AEs, study medication-related AEs, AEs leading to withdrawal and AEs leading to death.

Summary of AEs by Severity of Event

The number and percentage of subjects reporting AEs, and study medication-related AEs, will be summarized by the system organ class and by the preferred term. The severity of event will be recorded once per subject for each term as the maximum severity experienced by each subject (i.e. where the order of most severe to least severe is given by: severe, moderate and then mild).

Summary of AEs by Causality

The number and percentage of subjects reporting AEs will be summarized by the system organ class and by the preferred term. The causality will be recorded once per subject for each term giving the most likely relationship to study medication (i.e. in the order: very likely/certain, probable, possible, unlikely and then unrelated).

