4.3. Scheduled Visits

For full details of assessments performed at scheduled visits see flow chart in [Appendix G](#).

Each subject will undergo a total of 9 visits. Subjects' eligibility will be assessed at Screening (Visit 1), which can occur up to 28 days prior to dosing. Following a repeat eligibility check at Day 0 (Visit 2), eligible subjects will be randomized and dosed with the randomized treatment (BPL HRIG /vaccine or Comparator HRIG/vaccine on Day 0. Further administration of rabies vaccine, PK sampling and safety assessments will be conducted on Days 3 (Visit 3), 5 (Visit 4) (PK sampling only), 7 (Visit 5), 14 (Visit 6) and 28 (Visit 7). An additional visit for PK sampling and safety assessment will take place on Day 49 (7 weeks/Visit 8) and Day 140 (20 weeks/Visit 9). The last visit will be the End-of-Study Assessment which will take place on Day 140 (20 weeks). This visit will comprise the final PK sample and safety assessments. The end of the trial is defined as the last subject's last End-of-Study Assessment (or the date of their last data collected, if the subject has an AE at the End-of-Study Assessment that needs to be followed, see [Appendix A](#) section 4).

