8.2.1. Adverse Events

All adverse events that appear or worsen during the study, from the time of signing informed consent, will be recorded in the CRF. If a subject has a recurring condition, then this should be recorded at the Screening Visit in the Medical History pages of the CRF. Fluctuations or re-occurrences of the condition, that are considered normal for that subject and are recorded in the medical history, and need not be reported as an adverse event. However, if the condition were to deteriorate during the study this would then be recorded as an adverse event.

Adverse events will be reported in terms of their type, duration, treatment and/or severity.

For further information on the definition and reporting of adverse events, see [Appendix A](#).

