2.3 Clinical Laboratory and Other Adverse Events

If a laboratory result is considered by the investigator to be clinically significant or have a clinically significant pathological change from baseline it should be recorded as an AE.

Other abnormal results (e.g. x-rays, scans, physical examination findings) that worsen from baseline and/or are considered clinically significant should also be recorded as AEs.

The investigator will exercise his or her medical and scientific judgment in deciding whether an abnormal laboratory finding or other abnormal assessment is clinically significant.

AEs should be reported and documented in accordance with the procedures outlined below. All AEs occurring during the study must be documented on the relevant CRF/e-CRF pages. The following data should be documented for each AE:

- Description of the symptom event
- Classification of 'serious' or 'not serious'
- Severity
- Date of first occurrence and date of resolution (if applicable)
- Action taken
- Causal relationship
- Outcome of event (unknown, recovered, not recovered, recovered with sequelae, death [with date and cause reported])

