3.1 Causality

All AEs will be recorded in the CRF/eCRF, whether considered to be related or unrelated to the treatment. The record will include the following: brief description of event (preferably a diagnosis), date and time started and stopped severity, outcome, actions taken and classification of the AE. The Investigator should also evaluate the probability of a causal relationship of the AE to each medication administered during the study according to the following criteria as:

-
1. Unrelated Clinical event with an incompatible time relationship to study medication administration, or that could be explained by underlying disease or other drugs or chemicals, or is incontrovertibly not related to the IMP.
 2. Unlikely Clinical event whose time relationship to study medication administration makes a causal connection improbable, but that could plausibly be explained by underlying disease or other drugs or chemicals.
 3. Possible Clinical event with a reasonable time relationship to study medication administration, but that could also be explained by concurrent disease or other drugs or chemicals.
 4. Probable Clinical event with a reasonable time relationship to study medication administration, and is unlikely to be attributed to concurrent disease or other drugs or chemicals.
 5. Very likely / certain Clinical event with plausible time relationship to study medication administration, and that cannot be explained by concurrent disease or other drugs or chemicals.

Study medication is defined as those investigational compounds or their controls and vaccines used in the study.

It will be assumed that for all adverse events classified as “probably related”, “possibly related” or “very likely / certainly related” to the study medication, there is reasonable likelihood that the adverse event was causally related to the product. All such adverse events will be regarded as “causally related” to the study medication.

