5. The geometric mean titers (GMTs) for anti-rabies antibody titer at Visit 6-9 will be compared between treatment groups. Descriptive statistics and visual inspections will be reported as appropriate. No formal hypotheses testing will be performed.

g. EXPLORATORY PK ANALYSES

The following PK parameters for anti-rabies antibody concentrations will be summarized for both treatment groups:

- C_{\max} [IU/mL]
- T_{\max} [day]
- area under the concentration vs time curve to the last measurable concentration (AUC_{0-t}) [day*IU/mL]
- apparent terminal rate constant (λ_z) [day⁻¹]
- AUC_{0-7d} [day*IU/mL]
- area under the concentration vs time curve to infinity ($AUC_{0-\infty}$), if appropriate

- $C_{\max}/AUC_{0-\infty}$ [or C_{\max}/AUC_{0-t} if $AUC_{0-\infty}$ cannot be estimated]
- half-life ($t_{1/2}$), if appropriate

Non-compartmental PK methods will be utilized to calculate the subject level PK parameters. C_{\max} , AUC_{0-t} , AUC_{0-7d} , $AUC_{0-\infty}$, apparent terminal rate constant (λ_z), and $t_{1/2}$ will be dose normalized by dividing the raw PK parameters by the actual dose the subject received. A t-test will compare the PK and dose-normalized PK parameters between treatment groups. Log-transformations will be performed as necessary during statistical analysis when appropriate.

h. ADVERSE EVENT REPORTING

Adverse events (AEs) will be reported by the MedDRA system organ class and preferred term. Only treatment emergent AEs (i.e. beginning after dosing with BPL HRIG / vaccine or comparator HRIG / vaccine) will be included in the summary tables. All AEs will be included in the data listings.

Treatment-related AEs will be defined as events recorded as having a possible, probable or very likely/certain causality to treatment. AEs leading to withdrawal will be defined as events where the subject's participation in the study was discontinued as a result of the AE.

AEs will be summarized descriptively for all subjects and by treatment group. The denominator used for the calculation of percentages will be the number of subjects in the safety population per treatment group. For all AE summaries described below, counting will be performed by subject and event. For counts by subject, subjects experiencing the same event more than once will have that event counted only once within each system organ class and once within each preferred term.

The following summaries of treatment-emergent AEs will be provided:

SUMMARY OF AEs

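### Both documents define treatment-emergent AEs by onset alone, so an AE that starts before dosing and worsens afterwards can drop out of every AE summary table

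*Protocol*

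**What the plan says.** Collection starts at consent. Protocol section 8.2.1: "All adverse events that appear or worsen during the study, from the time of signing informed consent, will be recorded in the CRF". Section 4.3 fixes how early that can be: "Subjects' eligibility will be assessed at Screening (Visit 1), which can occur up to 28 days prior to dosing". The flow chart in Appendix G also has an AE check in the Day 0 pre-dose column.

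Tabulation is narrower. Protocol section 10.6.1: "Only treatment-emergent AEs, defined as those events with onset date from dosing with BPL HRIG" with vaccine, or comparator HRIG with vaccine. SAP section 8.h: "Only treatment emergent AEs (i.e. beginning after dosing with BPL HRIG / vaccine or comparator HRIG / vaccine) will be included in the summary tables". Both documents then list all AEs.

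On conditions already in the medical history, section 8.2.1 says: "if the condition were to deteriorate during the study this would then be recorded as an adverse event".

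The two lists of AE data items differ on timing. Appendix A section 2.3 asks for: "Date of first occurrence and date of resolution (if applicable". Appendix A section 3.1 asks for: "date and time started and stopped severity, outcome, actions taken and classification of the AE". The time of the HRIG injection is recorded under section 6.3.

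**The concern.** The usual purpose of a treatment-emergent definition is to capture what appears or gets worse under treatment. Here the collection rule has both parts and the tabulation rule has only the first. An AE that begins between consent and dosing and becomes more severe or serious after HRIG or vaccine may therefore never reach a table.

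The AE tables cover incidence, maximum severity, causality, serious AEs, AEs leading to withdrawal and AEs leading to death. Protocol section 10.6 bases the safety evaluation on inspecting summaries for imbalance between the groups, so an event found only in a listing falls outside the planned comparison. This matters for Objective 4 because section 2.5 states that BPL HRIG has had no clinical trials.

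The situation is plausible in this trial. Section 7.3.1 leaves room for dosing during a minor illness. The expected reactions in sections 2.6 and 2.8 include headache, fatigue and malaise, which a subject may already have before the injection.

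**Working it through.** The point concerns a classification rule, so there is no plan figure to reproduce. The check applies each wording to hypothetical records.

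| Hypothetical record | Protocol 10.6.1 | SAP 8.h |
|---|---|---|
| A. Headache starts Day -5, mild; Grade 3 on Day 1; kept as one record | Not emergent | Not emergent |
| B. Same course, but closed and re-entered as a new AE dated Day 1 | Emergent | Emergent |
| C. Medical-history condition deteriorates on Day 1; AE onset set at the deterioration | Emergent | Emergent |
| D. Bruise from a blood draw 20 minutes before HRIG on Day 0 | Not emergent by time; emergent by calendar date | Not emergent |
| E. Event on Day 0, onset time missing | Emergent by calendar date; otherwise undetermined | Undetermined |

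**A against B.** The same clinical course is tabulated or not, depending on how it is entered. The documents do not say which entry is required:

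- The deterioration sentence in section 8.2.1 follows from recurring conditions entered in the medical history at Screening. It does not address an AE that began after consent.
- The worsening clause in Appendix A section 2.3 concerns abnormal findings such as scans, X-rays and physical examination, not symptoms.
- Sections 7.4.1 and 7.5 to 7.7 have staff ask about AEs that are new or have changed, so a change would be noticed. No section says that a rise in severity opens a new record.
- A record described by its date of first occurrence, as in Appendix A section 2.3, points towards A.

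**C.** Setting the onset at the deterioration is implied by section 8.2.1 but not stated. On that reading the medical-history route is covered, and the gap is confined to AEs with onset between consent and dosing.

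**D and E.** The protocol speaks of an onset date and the SAP of beginning after dosing. With times available for both the event and the injection, the two agree on D. They part only if the protocol rule is programmed on the date alone. E has no rule in either document.

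**Size.** The documents give no rate of AEs before dosing, of their persistence to dosing or of their later worsening, so no expected count can be derived. The only available scale is one subject in a planned arm: 1/81 = 0.0123, or 1.2%.

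**The case against.** The best reply has four parts.

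1. *The loss depends on data entry.* Section 8.2.1 covers events that appear or worsen, which can be read as making a worsening recordable in its own right, and eCRF instructions outside these documents may already require a new line. This stands as a condition: the omission occurs when the AE is kept as one record. But nothing in either document excludes that entry, and the tabulation rule would then leave the event out.

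2. *Few events qualify.* The AE must start after consent, be ongoing at dosing, survive the repeat eligibility check and then worsen. Fever or acute illness on Day 0 is grounds for rescheduling, and medical-history conditions are handled separately. This stands, and it limits the importance of the point.

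3. *Little else is touched.* A reader might infer that every safety table is affected. The documents do not support that. Injection-site, serology, laboratory, hemolysis, vital-sign and physical-examination summaries do not use the treatment-emergent rule (Protocol sections 10.6.2 to 10.6.7). SAEs are reportable from consent under Appendix A section 5, whether or not they are emergent. Safety is descriptive, so no test or error rate changes.

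4. *The Day 0 difference is a matter of reading.* A reader might infer that the protocol counts events before the injection as emergent. The protocol ties onset to dosing, the times are collected, and section 10.3 refers to the SAP for further detail. The difference arises only under a date-level reading. Pre-dose procedures also precede randomization, so such events cannot depend on the assigned product.

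**Conclusion.** The concern holds in a limited form. Both definitions rest on onset alone. An AE that starts between consent and dosing and worsens or becomes serious after dosing, if kept as one record, is left out of all AE summary tables and appears only in the listings. The wordings also differ enough that a Day 0 event before the injection could be classified in two ways if the protocol rule is applied by calendar date, and neither document has a rule for a missing Day 0 time.

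The conclusion assumes that a worsening AE keeps its first onset. It does not extend to other safety tables or to deterioration of medical-history conditions. A reader might also want a number of affected subjects, but any such figure would rest on assumed rates that the documents do not supply. The primary endpoint and sample size are not involved. The change is still worth making, because the rule as written can remove an event the AE tables exist to show.

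**What to change.** Put one definition in Protocol 10.6.1 and SAP 8.h:

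> A treatment-emergent AE is any AE with onset date and time at or after the start of the Day 0 HRIG injection, or any AE with earlier onset that increases in severity grade or becomes serious after that time. If the Day 0 onset time is missing, the AE is treated as emergent.

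The HRIG injection is a natural anchor because section 7.3.2 has it given before the first vaccine dose.

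Use a single recording mechanism so that each worsening is counted once. For an AE with pre-dose onset only, close the existing record and open a new AE line dated at the post-dose worsening. Count only the new line as emergent. Making the first record emergent as well would double the event count. Do not split AEs that start after dosing, since that would inflate counts for ordinary changes in grade.

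Align Appendix A section 2.3 with section 3.1 so that both ask for a start time.

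The cost is wording in two documents and an eCRF completion instruction. AE start time and injection time are already specified for collection. Reported AE counts may rise slightly.

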6. INVESTIGATIONAL AND AUXILIARY MEDICINAL PRODUCTS

In this study, 'study medication' is defined as all products administered: BPL HRIG, comparator HRIG, and active rabies vaccine.

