7.4.1. Before Dosing

The following assessments will be performed at all visits:

- Check for any new or changed adverse events and concomitant medications since the last visit
- Oral temperature. If the participant is febrile (oral temperature $>38.0^{\circ}\text{C}$ (100.4°F) or has an acute illness, active rabies vaccine must not be given. The subject may continue in the study but should receive no further doses of active rabies vaccine and will not be eligible for the per protocol population.

- Injection site assessment (only if symptoms were observed at the previous visit)
- Blood samples will be taken for rabies virus neutralizing antibodies (see [Section 8.1.4](#))

Reserve blood samples will be taken (see [Section 7.9.1](#))

In addition, the following assessments will be performed at the specified visits (see also the Schedule of Assessments in [Appendix G](#)):

- Vital signs: sitting blood pressure (mmHg) after a 5-min rest, pulse rate and respiration rate – Day 28 (see [Section 8.2.8](#))
- Blood samples will be collected for the following assessments:
 - markers of hemolysis (DCT, LDH, plasma free hemoglobin, serum haptoglobin and serum bilirubin) on Day 3. These tests including CBC may be repeated on Day 5, Day 7 and Day 14 depending on results obtained at the previous visit (see [Section 8.2.7](#)).
- A urine sample for hemosiderin – Day 3. This test may be repeated on Day 5, 7 and Day 14 depending on results obtained at the previous visit (see [Section 8.2.7](#)).

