8.2.8. Vital Signs and Body Temperature

Vital signs will be assessed at Screening, Day 0, Day 28, and Day 49 and at the End-of-Study Assessment. Vital signs will include the following assessments:

- Sitting blood pressure (mmHg) after a 5-min rest.
- Pulse rate (bpm).
- Respiration rate (breaths/respirations per minute).

Results at the Screening Visit will be used to determine eligibility for the study. Evidence of uncontrolled hypertension (systolic blood pressure of >150 mmHg, and/or diastolic blood pressure of >100 mmHg), or heart rate >120 beats/min will exclude the subject from the study.

Oral body temperature will be assessed pre-dose on Days 0, 3, 7, 14 and 28. If the subject is febrile (oral temperature $>38.0^{\circ}\text{C}$ [100.4°F]) or has an acute illness at Day 0, their enrollment must be re-scheduled (see [Section 7.3.1](#)). If re-scheduled, Day 0 must be within 28 days of all screening procedures; if outside of this window the subject must undergo a repeat screening visit. A new subject number will be assigned. (See SRM for instructions on repeat screening).

If the subject is febrile at any subsequent visit, active rabies vaccine must not be given. The subject may continue in the study but should receive no further doses of active rabies vaccine and will not be eligible for the per protocol population.

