9. WITHDRAWAL OF SUBJECTS

Subjects may stop study treatment for any of the following reasons:

- Withdrawal of consent.
- Significant protocol deviation.
- Occurrence of an adverse event which interferes with the subject's ability to continue in the trial.
- Occurrence of adverse events (AEs) not compatible with the continuation of subject participation in the study, in the investigator's opinion (e.g. anaphylactic or other severe/serious reaction to injection).
- Investigator's request.
- Pregnancy. If pregnancy occurs, the subject should be monitored and the outcome of delivery reported.
- Requirement for therapeutic intervention prohibited by the protocol, for example, immunosuppressive agents.
- Potential exposure to the rabies virus during the study, which would necessitate treatment with licensed HRIG.
- Presenting with fever (oral temperature $>38.0^{\circ}\text{C}$ [100.4°F]) on Day 3, 7, 14 or 28.
- Premature termination of the trial by BPL (e.g. if special circumstances concerning the IMP or BPL occur, making further treatment of subjects impossible, or if serious adverse events occur that are considered to make further treatment of subjects impossible). If this occurs, BPL or BPL's representatives will notify the regulatory authorities, ethics committees and investigators of the reason for premature study termination, within 15 days from the study being halted.
- Reason not provided (subject lost to follow-up)

The clinical investigator may also remove a subject if, in his/her opinion, it is in the best interests of the subject. In exceptional circumstances relating to safety, the sponsor may withdraw subjects at any time.

Subjects are free to withdraw from the study at any time without providing reason(s) for withdrawal and without prejudice to further treatment. The reason(s) for withdrawal will be documented where possible, particularly where withdrawal is a consequence of an adverse event (see [Appendix A](#)). The subject's primary care physician will be informed of the reason for withdrawal if follow-up care is needed for safety. The subject will be informed if this is required.

Data collected up until a subject's withdrawal from the study will be used in the analysis. Data on screen failures will be collected.

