3.3 Action taken

The action taken by the Investigator or study staff should be documented as:

- Drug withdrawn
- Dose reduced
- Dose increased
- Dose not changed
- Unknown

-
- Not applicable

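### The only discontinuation row in the AE overview is defined by leaving the study, so it omits subjects whose vaccine course is stopped for fever or acute illness but who stay in follow-up

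*Protocol*

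**What the plan says.** Protocol 10.6.1 defines AEs leading to withdrawal as events where the subject's "participation in the study was discontinued as a result of the AE". SAP 8.h uses the same definition. The planned overview, by subject and by event, has rows for all AEs, serious AEs, medication-related AEs, AEs leading to withdrawal and AEs leading to death. The withdrawal row is the only one about discontinuation, and neither document plans a summary by action taken.

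Protocol 7.4.1 governs the vaccine visits on Days 3, 7, 14 and 28. If the subject is febrile or "has an acute illness, active rabies vaccine must not be given". It then adds: "The subject may continue in the study but should receive no further doses of active rabies vaccine". Section 8.2.8 has the same rule for fever only: "If the subject is febrile at any subsequent visit, active rabies vaccine must not be given".

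Section 6 includes the rabies vaccine in its definition of study medication. Section 9 carries the title Withdrawal of Subjects but opens with "Subjects may stop study treatment for any of the following reasons", and its list includes "Presenting with fever" on any of the four later vaccine days. Appendix A 2.3 requires the action taken to be documented for each AE, and Appendix A 3.3 gives six options for it, one of which is "Drug withdrawn".

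**The concern.** The protocol creates a group of subjects whose treatment has ended but whose participation has not. The AE overview recognises only the second kind of ending.

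Objective 4 covers tolerability, and Section 10.6 says the safety evaluation will look through the summaries for clinically relevant imbalance between arms. Fever is listed among the HRIG class effects (Table 3) and among the common reactions to the vaccine (Section 2.8), so the trigger bears on tolerability. A reader of the overview would take the withdrawal row as the number of subjects who could not complete treatment because of an AE. As defined, it does not give that number.

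**Working it through.** The documents contain no figure for this point, so the check sets the passages against each other and then shows the size under a stated assumption.

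**1. Does stopping vaccine end treatment?** HRIG is given once, on Day 0 (Section 6.2). Vaccine is given on Days 0, 3, 7, 14 and 28, five doses in all. After Day 0, vaccine is the only study medication left to stop.

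| Visit at which vaccine is stopped | Doses already given | Doses not given (5 minus given) |
|---|---|---|
| Day 3 | 1 | 4 |
| Day 7 | 2 | 3 |
| Day 14 | 3 | 2 |
| Day 28 | 4 | 1 |

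Under 7.4.1 the stop is permanent, so each line is a true end of treatment.

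**2. Who falls outside the row?**

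| Situation | Source | In the withdrawal row? |
|---|---|---|
| Fever at a vaccine visit, vaccine stopped, subject stays | 7.4.1, 8.2.8 | No |
| Acute illness at a vaccine visit, vaccine stopped, subject stays | 7.4.1 | No |
| Fever recorded as an AE, and the site ends participation because of it | Section 9 | Yes |
| AE that prevents the subject from continuing in the trial | Section 9, AE bullets | Yes |

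Lines 1 and 3 can describe the same clinical event handled differently by two sites.

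**3. Where do the omitted events still appear?** If recorded as treatment-emergent AEs, they are in the overall, severity and causality summaries, and all AEs are listed (10.6.1). All data are listed (10.3).

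**4. Can they be identified from planned data?** Partly, from each of three sources.
- Action taken is recorded for each AE. However, the documents do not say which of the six options applies when a scheduled vaccine dose is withheld, and the options do not name the product.
- The date of each vaccine dose given is recorded (Section 6.3), so a missing dose is visible, but that list does not include a reason.
- Oral temperature is measured before each vaccine dose (8.2.8). A reading above 38.0°C need not become an AE record, because Appendix A 2.3 and 3 leave clinical significance to the investigator.

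Action taken therefore has to be cross-checked against the vaccine record.

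**5. Size.** With *k* subjects in an arm of 81 (Section 5.1) who stop vaccine for an AE and stay, the omitted share is *k*/81. The values of *k* are assumptions.

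| *k* | Share of arm | Contribution to the withdrawal row |
|---|---|---|
| 1 | 1/81 = 1.2% | 0 |
| 2 | 2/81 = 2.5% | 0 |
| 4 | 4/81 = 4.9% | 0 |
| 8 | 8/81 = 9.9% | 0 |

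**The case against.** The sponsor has several fair answers.

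- **The events are not lost.** They remain in the other AE tables and the listings, and a subject who misses any of the first three vaccine doses is also excluded from the primary PK population (10.4) and classed as a non-complier (10.7.2). This stands. The gap is in one row.
- **Section 9 ties AEs to participation.** A reader might infer that any AE that stops vaccine escapes the count. The documents do not support that: the AE bullets in Section 9 concern events that prevent the subject from continuing in the trial, and such events would be counted. Stopping vaccine while staying in the study is explicit only for fever and acute illness.
- **Some febrile subjects may be counted.** A reader might infer that every febrile subject contributes zero. That is true only of those who stay. Because Section 9 lists fever under withdrawal, the outcome may depend on how the site reads the protocol.
- **The stopping rule is not a pure measure of intolerance.** It requires no causal link, so a count of stops would include intercurrent illness. The same vaccine is given in both arms, and tolerability is also covered by the severity, causality and injection-site summaries. This stands, and it is a reason to show causality with the new row, not to leave the row out.

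What survives is that no planned summary shows treatment stopped for an AE when the subject remains in the study.

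**Conclusion.** The point holds as a minor reporting gap. In both documents the only discontinuation row is tied to leaving the study, and the protocol expressly lets subjects stop vaccine for fever or acute illness and stay. Those subjects are absent from that row.

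The number is unknown. The range of 1.2% to 9.9% per arm rests on assuming that 1 to 8 of 81 subjects are affected and that their fever or illness is recorded as an AE.

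A reader might go further and infer a bias between arms. Nothing in the documents shows one: the stopping rule is the same in both arms, and no rates are given. Nor can it be assumed that these cases will all carry the drug-withdrawn code, since no coding instruction is given. The primary analysis and its conclusion are unaffected.

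**What to change.** In Protocol 10.6.1 and SAP 8.h, before unblinding, replace the single category with two, tabulated by arm on the safety population:

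- **(a)** AEs leading to discontinuation of study medication, specifying vaccine. Identify these from the AE action-taken field and cross-check them against the vaccine administration record, not from the drug-withdrawn code alone.
- **(b)** AEs leading to withdrawal from the study, as now defined.

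Show causality for both, using the existing scale, so that intercurrent illness can be told apart from product intolerance.

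Section 9 must be reconciled with 7.4.1 and 8.2.8 on whether a febrile subject is withdrawn or may continue, so that all sites classify these cases in the same way. Which rule applies is for the sponsor to settle.

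The cost is one extra row, a change of wording in both documents and a cross-check of data already collected. The downside is a higher reported discontinuation rate, part of which will be intercurrent illness. Sample size, alpha and visits do not change.
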